3.1.4 Per Protocol Cognition (PPc) Analysis Set

The Part A PPc Analysis Set will comprise of all patients in the ITT Analysis Set who received all doses of study medication (on V1, V4, V7, V10, V13 and V18 in Part A), have attended the safety visit after booster (V20 in Part A), have no major protocol deviations that could affect the efficacy analyses or major protocol deviations that have been classified as “Use of disallowed concomitant medication”, relating to use of Anti-Alzheimer Disease medication.

Analysis of secondary efficacy endpoints relating to the assessment of cognition and quality of life in Part A will be repeated using the Part A PPc Analysis Set.

The Part B PPc Analysis Set will comprise of all patients in the ITT Analysis Set who received all doses of study medication (on V1B, V4B, V7B, V10B, V13B and V18B in Part B), have attended the safety visit after booster (V20B in Part B), have no major protocol deviations that could affect the efficacy analyses or major protocol deviations that have been classified as “Use of disallowed concomitant medication”, relating to use of Anti-Alzheimer Disease medication.

During the blind review meeting, decisions will be made regarding the PPc Analysis Set in terms of whether deviations in Part A affect Part B for inclusion in analysis set.

Analysis of secondary efficacy endpoints relating to the assessment of cognition and quality of life over the entire duration of the study (Parts A and B combined), will be repeated using patients who are in Part A PP/PPc Analysis Set and the Part B PP/PPc Analysis Set. (See Section [3.1.3](#))

Patients will be analyzed according to their randomized treatment assignment, regardless of the treatment received.

3.1.5 Safety Analysis Set

The Safety Analysis Set will include all randomized patients who received any study treatment. All safety analyses will use the Safety Analysis Set. Patients will be analyzed according to the treatment received, regardless of the treatment assigned.

3.2 Determination of Sample Size

For the primary safety endpoint, the sample size was determined to ensure the probability of detecting an AE that occurs with a minimum rate of 5% within the ABvac40 treated dose cohort is greater than 95%. Using Hanley's [1] simple approximation, a minimum of 60 patients per treatment group is required, i.e., total study sample size of 120 patients.

The total sample size of 120 patients, when considering a dropout rate of 40% during the clinical trial, should result in approximately 70 patients completing the study. In assessing the primary efficacy endpoint of no difference in the mean maximum change from baseline in anti-A β 40 antibody signal (OD), a one-sided t-test with a significance level of 0.025 will be employed. Assuming a difference of 1.778 O.D. between the active group and placebo group means with associated standard deviations of 2.0 and 1.0, respectively, there is greater than 85% power to reject the null hypothesis of no difference in the mean maximum change from baseline in anti-A β 40 antibody signal between the treatment groups. It should be further noted that the study may be insufficiently powered to demonstrate efficacy in clinical or other biomarker outcomes.

3.3 Treatment Misallocations

For patients with errors in treatment allocation, they will be reported for efficacy and safety analyses as follows:

If a patient is:

- Randomized and not treated (treatment is defined as exposure to study treatment) then by definition they will be excluded from the efficacy and safety analyses as actual treatment is missing.
- Treated but not randomized, then by definition they will be excluded from the efficacy analyses since randomized treatment is missing, but they will be reported under the treatment actually received for all safety analyses.
- Randomized but received incorrect treatment at any time during the study, then they will be reported under their randomized treatment group for all efficacy analyses. For all safety analyses, they will be reported under the actual treatment received. If a patient received both ABvac40 and placebo throughout the trial, they will be reported under the ABvac40 treatment group for all safety analyses other than summaries of AEs. Details of how AEs will be reported in such circumstances are provided in section 7.2.1 below.

3.4 Protocol Deviations

All protocol deviations relating to parts A and B of the study will be categorized as major or minor and assessed at a data review meetings prior to DBL for parts A and B respectively, to determine the impact of each on the PP and PPe Analysis Sets.

4 STUDY VARIABLES

4.1 Safety Variables (Part A and Part B)

4.1.1 Primary Safety Variable – Adverse Events

AEs experienced by the patients will be collected throughout the entire study and will be coded using version 20.0 of the Medical Dictionary for Regulatory Activities (MedDRA). Serious AEs of special interest (SAESIs) will be defined as:

- Amyloid Related Imaging Abnormalities (ARIA), either
 - ARIA-micro-hemorrhage (ARIA-H), or
 - ARIA-vasogenic edema and/or sulcal effusion (ARIA-E)

- Aseptic Meningo-Encephalo-Myelitis

4.1.2 Secondary Safety Variables

- Withdrawal criteria (study continuation decision)
- Physical examination:

Complete physical examinations will be performed at all face-to-face visits. These assessments include examination of the neck (including thyroid), eyes, ears, throat, abdomen, skin/mucous membranes, and cardiovascular, respiratory, genito-urinary, and musculoskeletal systems.

- Neurological examination:
Neurological examinations are performed at all face-to-face visits. These assessments include cortical function, cranial nerves, motor function, reflexes, sensory function, gait, and posture.

- Concomitant medication
Each medication will be coded to Anatomical Therapeutic Chemical (ATC) classification codes using the World Health Organization Drug classification Dictionary (WHO-DD), version WhoDrug B2 2017Q3 and defined as either a prior or concomitant medication, depending on the start and end dates of the medication, relative to the date of first dose of study treatment.

Prior medications will be defined as any medication ended prior to the first dose of study treatment.

Concomitant medications will be defined as any medication started on or after the start of study treatment or any medication taken prior to the start of study treatment and continued after the start of study treatment.

- Vital signs:
The following vital signs parameters will be monitored: blood pressure, heart rate, respiratory rate, body temperature).

- Electrocardiogram (ECG):
The following ECG parameters will be recorded: HR, PR interval, QRS and QT.

- Laboratory Assessments:
Laboratory assessments will be performed for the following: Hematology, Toxicology (reactive protein), Biochemistry, Coagulation, Serology and Urine sampling. Appendix 9.3 provides a list of that laboratory test parameters that will be recorded.

4.2 Efficacy Variables (Part A and Part B)

4.2.1 Primary Outcome Variable

Maximal increment ($M\Delta$) of anti- $A\beta$ 40 antibody signal (estimated by ELISA (signal OD values) in each patient, from baseline.

4.2.2 Secondary Outcome Variables

4.2.2.1 Characterization of Immune Response

- Levels of anti-keyhole limpet hemocyanin (KLH) (Part A and Part B) and anti- $A\beta$ 42 antibodies in plasma (Part A only - anti- $A\beta$ 42 antibodies in plasma are not analysed by Araclon)
- Level of anti- $A\beta$ 40 antibodies in Cerebrospinal Fluid (CSF)
- Level of anti- $A\beta$ 40 antibodies in plasma

- Analysis of the peripheral blood cell subsets by immunophenotyping – Part A only (not analysed by Araclon)
- Levels of antibody secreting cells (only analysed in Part A and not analysed in Part B)
- Levels of cytokine-secreting cells (IFN- γ and IL-4) – Part A only (samples from only a small number of patients were analyzed. Hence, data for this analysis will not be reported)

4.2.2.2 Assessment of disease biomarkers:

- Levels of A β 40 and A β 42 peptides in plasma
- Cortical fibrillary amyloid deposition assessed by a-PET scans.
- Levels of CSF biomarkers [A β 42, A β 40 (Part A and B) and Tau, P-tau, neurofilament light and neurogranin (Tau, P-tau, neurofilament light and neurogranin were only analysed in Part A and were not analysed in Part B)] and other A β peptide species (other A β peptide species were not analysed by Araclon) (Part A and Part B)
- Brain volumetric changes (including hippocampal and ventricle changes) and atrophy of the hippocampus using MRI.

4.2.2.3 Assessment of cognition and quality of life:

- Mini Mental State Examination (MMSE):
 - an 11-question measure that tests five areas of cognitive function: orientation, registration, attention and calculation, recall, and language. The maximum score is 30. A score of 23 or lower is indicative of cognitive impairment
 - the following parameters will be summarized/analyzed as outlined in section 6.3:
 - total MMSE score
- Clinical Dementia Rating (CDR) scale:
 - a 5-point scale used to characterize six domains of cognitive and functional performance applicable to Alzheimer disease and related dementias: Memory, Orientation, Judgment & Problem Solving, Community Affairs, Home & Hobbies, and Personal Care.
 - the following parameters will be summarized/analyzed as outlined in section 6.3:
 - CDR-Sum of Boxes (CDR-SB), derived as the sum of the six individual domain scores and can range from 0 to 18.
 - Global CDR, as recorded on a scale of 0–3: no dementia (CDR = 0), questionable dementia (CDR = 0.5), MCI (CDR = 1), moderate cognitive impairment (CDR = 2), and severe cognitive impairment (CDR = 3).
- Repeatable Battery for the Assessment of Neuropsychological Status (RBANS):
 - assesses five cognitive domains, i.e., Immediate Memory, Visuospatial/constructional, Language, Attention, and Delayed Memory. The test consists of 12 subtests and the score on each subtest contributes to one of the five domains.
 - the following parameters will be summarized/analyzed as outlined in section 6.3:
 - Scores derived for each of the five domains
 - Total score, which can range from 40 to 160, derived as the sum of the five domain scores.
- Alzheimer's Disease Cooperative Study – Activities of Daily Living (ADCS-ADL), MCI:
 - a 24-item scale that includes 6 basic activities of daily living (BADL) items and 16 instrumental activities of daily living (IADL) items that provide a total score from 0–78, with a lower score indicating greater severity
 - the following parameters will be summarized/analyzed as outlined in section 6.3:
 - ADCS-ADL-MCI (item 1-24) total score
- Columbia Suicide Severity Rating Scale (C-SSRS)
 - The following parameters will be summarized as outlined in section 6.3:

- Most severe ideation (on a scale of 0 to 5)
- Suicidal behaviour (yes/no)
- Trail Making Test (TMT)
 - consists of two parts in which the patient is instructed to connect a set of 25 dots as quickly as possible while still maintaining accuracy. There are two parts to the test: in the first, the targets are all numbers from 1 to 25 and the test taker needs to connect them in sequential order; in the second part, the dots go from 1 to 13 and include letters from A to L.
 - the following parameters will be summarized/analyzed as outlined in section 6.3:
 - Time required to complete trail A.
 - Time required to complete trail B.
- Investigator Global Evaluation (IGE)
- EuroQol 5 Dimensions (EQ-5D-5L)
 - comprises of 2 sections: a descriptive system questionnaire and a Visual Analogue Scale (VAS).
 - the EQ-5D-5L descriptive system comprises of 5 dimensions (mobility, self-care, usual activities, pain/discomfort, anxiety/depression), with each dimension measured on the following increasing scale of severity: 1=no problems, 2=slight problems, 3=moderate problems, 4=severe problems, and 5=extreme problems.
 - the following parameters will be summarized/analyzed as outlined in section 6.3:
 - Overall severity index (SI), calculated for each patient, at each visit as:
$$SI = [100 - (\sum s_i - 5) \times 5]$$
, where s is the severity recorded for dimension i .
 - Visual Analogue Scale (VAS), recording the patient's self-rated health on a vertical scale, ranging from 100 = 'Best imaginable health state' down to 0 = 'Worst imaginable health state'.

5 SUMMARY OF STUDY POPULATION

5.1 Patient Disposition

The following disposition information will be summarized for all patients screened:

- The number of patients screened
- The number of patients who screen failed (patients who fail screening once, are re-screened, and are treated in the study are counted as screen failures and as enrolled patients. Patients who fail screening twice are counted only once as screen failures.)
- The number of patients who received any study treatment in each of Part A and Part B.
- The number of patients who received all immunizations in each of Part A and Part B
- The number of patients in the Safety, ITT, mITT, PP and PPc Analysis Sets
- The number and percentage of patients who completed each of Part A and Part B of the study
- The number and percentage of patients who discontinued from each of Part A and Part B of the study and the reason for premature study discontinuation
- The distribution of the number of days relative to first dose of study treatment (i.e., date of discontinuation – date of first dose + 1) for patients who prematurely discontinue from each of Part A and Part B of the study

- The number and percentage of patients who continued into Part B of the study

A listing of patient disposition for all patients randomized will also be presented.

5.2 Protocol Deviations

Protocol deviations will be identified during the study and evaluated before the database lock. The type/category of protocol deviations and severity (i.e., minor and major) will be summarized and listed.

5.3 Demographics

Demographic characteristics including age, sex, race, tobacco usage (never, former current), alcohol usage (never, former, current), drug habit (never, former, current), highest level of education (some school, high school graduate, college graduate, university degree), baseline height, baseline weight and calculated baseline body mass index (BMI = baseline weight (kg)/baseline height (m)²) will be summarized by study treatment group for the ITT analysis set. Missing categories will be presented where necessary.

A listing of demographic characteristics will also be presented.

5.4 Baseline Disease Characteristics

Baseline disease characteristics (recorded during Part A): study disease (a-MCI or vm-AD), a-PET status, ApoE genotype and time from disease diagnosis (days from diagnosis to signing of study informed consent) will be summarized by study treatment group for the ITT analysis set.

A listing of baseline disease characteristics will also be presented.

5.5 Medical History

Medical history will be coded using MedDRA version 20.0 and summarized by study treatment group, system organ class (SOC) and preferred term (PT) for the ITT analysis set.

A listing of patient medical history will also be presented.

6 EFFICACY ANALYSIS METHODS

6.1 Part A

6.1.1 Analysis of Primary Outcome Variable

Change in anti-A β 40 antibody signal from baseline to each post-baseline efficacy assessment visit will be calculated as: post-baseline OD – baseline OD.

The maximal increment ($M\Delta$) in anti-A β 40 antibody signal for a patient will be defined as the maximum change from baseline in anti-A β 40 antibody signal across all post-baseline visits. A comparison of the average $M\Delta$ in anti-A β 40 antibody signal between the ABvac40 and placebo groups will be performed using a one-sided t-test.

The trial will be considered successfully confirmatory regarding efficacy (immunogenicity) of ABvac40 if the average $M\Delta$ of anti-A β 40 antibody signal (OD in ELISA) in the ABvac40 group is significantly greater than the average $M\Delta$ of anti-A β 40 antibody signal in the placebo group. i.e.

- Null hypothesis: average $M\Delta$ anti-A β 40 (ABvac40) \leq average $M\Delta$ anti-A β 40 (placebo)
- Alternative hypothesis: average $M\Delta$ anti-A β 40 (ABvac40) $>$ average $M\Delta$ anti-A β 40 (placebo)

If the assumption of normality of the distribution of $M\Delta$ in anti-A β 40 antibody signal is violated, a Mann-Whitney U test will be used to compare the treatment groups.

In addition, the average $M\Delta$ of anti- $A\beta$ 40 antibody signal between the two treatment groups will be compared using an Analysis of Covariance (ANCOVA) model, using the $M\Delta$ anti- $A\beta$ 40 antibody signal as the dependent variable, baseline anti- $A\beta$ 40 antibody signal (OD in ELISA) as covariate and treatment group and amyloid positivity as fixed effects.

The number and percentage of patients reaching a value greater than or equal to the treatment $M\Delta$ will be tabulated by treatment group for each visit.

$M\Delta$ negative values will not be imputed to zero.

The number and percent of Positive Responders/Non-Responders will be presented for the ABvac40 treatment group, by visit.

Each analysis will be performed using the mITT Analysis Set. In addition, a listing of anti- $A\beta$ 40 antibody signal will be presented, along with the calculated change from baseline and a flag/flags indicating the maximal increment(s) for each patient.

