7.2.1.1 Assessment and characterization of the immune response

For the assessment and characterization of the immune response blood samples will be collected at visits V0, V1, V3, V6, V9, V12, V15, V16, V17, V20, V21, V23 and V25 (Part A), and at visits V1B, V3B, V6B, V9B, V12B, V15B, V16B, V17B, V20B, V21B and V22B (Part B). All these analysis, together with the levels of A β peptides in plasma, will be centralized at the Araclon-Grifols.

The laboratory tests to be performed with these samples are listed below. (Detailed descriptions of the laboratory test procedures are located in the study Laboratory Manual document):

- Characterization of the antibodies generated by vaccination with ABvac40: it will proceed to the titration of antibodies generated against the immunogenic peptide (A β x-40), other vaccine components (KLH) and A β -42 peptide. The specificity and isotype of these antibodies will also be characterized. These analyzes will be carried out in plasma samples by Enzyme-Linked ImmunoSorbent Assay (ELISA).

For the Part A, patients in the verum group will be classified as “Positive Responders” when their maximal increment ($M\Delta$) of anti-A β 40 specific antibody signal (OD in ELISA) from the pre-treatment visit (either V0 or V1) is equal or greater than 3 times the standard deviation of the titration ELISA. The antibody titers (defined as the inverse of the maximal plasma sample dilution which showed an OD increase ≥ 3 SD with regard to the preimmune sample) of Positive Responder patients will be reported.

- Analysis of cytokines in plasma: quantitation of a panel of cytokines in order to characterize the type of immune response (Th1 or Th2) by sandwich ELISA [Part A].
- Analysis of antibody-secreting cells: quantitation of B-lymphocytes secreting antibodies against A β or other components of the vaccine. This analysis will be performed by Enzyme-Linked ImmunoSpot (ELISpot) assay.
- Analysis of cytokine-secreting cells: quantitation of cells secreting cytokines in order to characterize the potency and type of immune response (Th1 or Th2). This analysis will be performed by ELISpot assay [Part A].
- Immunophenotyping of circulating blood cells: Quantitation of the relative number of peripheral blood mononuclear cells (cluster of differentiations; CD) to monitor the effect of the vaccine at cellular level. This analysis will be performed by multicolor flow cytometry [Part A].

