9.1.2 Efficacy Analysis (Part A)

9.1.2.1 Primary Efficacy Analysis (immunogenicity)

The primary variable for immunogenicity is the average maximal increment ($M\Delta$) of anti- $A\beta$ 40 antibody signal (OD in ELISA).

For the comparison of the response to treatment between the verum and placebo group the maximal increment ($M\Delta$) of anti- $A\beta$ 40 antibody signal (OD in ELISA) with regard to the pre-treatment visit (either V0 or V1) in each subject will be used as a summary measure. The treatment comparisons will be carried out by one-sided t test or Mann-Whitney U test if variable has non-normal distribution.

The trial will be considered successfully confirmatory regarding efficacy (immunogenicity) of ABvac40 if the average maximal increment ($M\Delta$) of anti- $A\beta$ 40 antibody signal (OD in ELISA) in the verum group is >0 OD than the average $M\Delta$ in the placebo group. This primary efficacy analysis will be conducted in the overall study population.

- Null hypothesis: The average maximal increment ($M\Delta$) of anti- $A\beta$ 40 antibody signal (OD in ELISA) for the treated group is equal to that for placebo.
- Alternative hypothesis: The average maximal increment ($M\Delta$) of anti- $A\beta$ 40 antibody signal (OD in ELISA) for the treated group is >0 OD than the average $M\Delta$ in the placebo group.

The $M\Delta$ of anti- $A\beta$ 40 antibody signal between the two treatment groups will be compared using an Analysis of Covariance (ANCOVA) model, using the $M\Delta$ as the dependent variable, baseline anti- $A\beta$ 40 antibody signal (OD in ELISA) as covariate and the treatment group and

amyloid positivity as fixed effects. In addition, the number and percentage of patients in each visit reaching a value greater or equal than the $M\Delta$ will be tabulated by groups for each variable.

Patients in the verum group will be classified as “Positive Responders” when: i) their $M\Delta$ of anti-A β 40 antibody signal is equal or greater than 3 times the standard deviation of the titration ELISA and ii) more than the 50% of the signal in the visit reaching the $M\Delta$ is eliminated by pre-adsorption of the sample. The antibody titers, defined as the inverse of the maximal plasma sample dilution which showed an OD increase ≥ 3 SD with regard to the pre-immune sample (either V0 or V1), of “Positive Responder” will be reported.

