1.1 Purpose and Scope of Analysis Plan

The purpose of this statistical analysis plan (SAP) is to provide detailed information to aid in the implementation of the statistical analysis of the study data. It briefly summarizes the protocol, describes the analysis sets that will be analyzed, and describes the analyses to be performed. The details of the specific statistical methods that will be used are provided. Post database lock (DBL), it may become apparent that the planned analyses should be modified, e.g., modeling assumptions are untenable. Any modification to the original analysis plan will be identified and described in the clinical study report (CSR).

Table, figure, and listing specifications are in separate documents. This analysis plan is meant to supplement the study protocol. If differences occur between analyses described in the SAP and the current protocol, those found in this SAP will assume primacy.

This SAP is written with due consideration of the recommendations outlined in the most recent International Conference on Harmonisation (ICH) E9 Guideline entitled Guidance for Industry: Statistical Principles for Clinical Trials and the most recent ICH E3 Guideline, entitled Guidance for Industry: Structure and Content of Clinical Study Reports and will be finalized prior to DBL.

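### Positive Responders are to be reported for ABvac40 only, under a term the SAP does not define and the protocol defines in two ways, so the descriptive responder rate has no concurrent control

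*SAP*

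**What the plan says.** **Which arm.** SAP 6.1.1 plans one responder output: "The number and percent of Positive Responders/Non-Responders will be presented for the ABvac40 treatment group, by visit". Both protocol definitions are also limited to the vaccine arm. Section 7.2.1.1 says "patients in the verum group will be classified as" Positive Responders, and section 9.1.2.1 opens the same way: "Patients in the verum group will be classified as".

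**Which definition.** Protocol 7.2.1.1 sets one condition: the maximal increment "from the pre-treatment visit (either V0 or V1) is equal or greater than 3 times the standard deviation of the titration ELISA". Protocol 9.1.2.1 sets the same condition and adds a second: at the visit where the maximum occurs, more than half of the signal "is eliminated by pre-adsorption of the sample". The SAP uses the term without defining it, and SAP 9.2, which lists changes from the protocol analyses, does not mention it.

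**Over which visits.** SAP 6.1.1 defines the maximal increment as the largest change from baseline in "antibody signal across all post-baseline visits". The responder table, in contrast, is by visit.

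**What both arms get.** SAP 6.1.1 also plans a by-visit table, for each treatment group, of patients at or above the treatment's maximal increment. It further plans a listing of OD, change from baseline and each patient's flagged maximum. Neither applies the responder rule.

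**The concern.** A responder proportion is easily read as the share of patients in whom the vaccine worked. That reading needs two things the plan does not provide.

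The first is a single definition. A patient whose increment passes 3 SD but whose signal is not mostly removed by pre-adsorption is a responder under 7.2.1.1 and a non-responder under 9.1.2.1. Both sections also say that titers will be reported for responders, so the choice decides whose titers appear.

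The second is a control. A threshold applied to the largest of several noisy changes is crossed by some patients who have no response at all. Placebo patients are sampled at the same visits and would show how often this happens, but no output applies the rule to them.

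The by-visit layout adds a third uncertainty. A per-visit rate and an ever-responder rate are different quantities with different noise floors, and the SAP does not say which one it means.

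**Working it through.** **1. Is there a figure in the plan to reproduce?** The documents give no false-positive rate for the criterion and no ELISA SD. The only responder figure is from Phase I (protocol 2.2): 87.5% of 16 verum patients, that is 14/16. It was described as a 3 SD rise at any visit, with no placebo rate. That is the 7.2.1.1 type of rule, applied as an ever-responder rule.

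**2. The definitions side by side**

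| | 3 ELISA SD | Pre-adsorption above 50% | Based on | Arm |
|---|---|---|---|---|
| Protocol 7.2.1.1 | yes | no | maximum | verum |
| Protocol 9.1.2.1 | yes | yes, at the visit of the maximum | maximum | verum |
| SAP 6.1.1 | not stated | not stated | by visit | ABvac40 |

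The SAP's precedence rule (1.1: "If differences occur between analyses described in the SAP and the current protocol, those found in this SAP will assume primacy") cannot settle this, because the SAP offers no definition to take precedence. Neither protocol section defines a per-visit responder.

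**3. Number of chances.** Protocol 7.2.1.1 lists post-baseline samples at V3, V6, V9, V12, V15, V16, V17, V20, V21, V23 and V25: 11 samplings. Patients who stop early have fewer.

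**4. How often noise alone meets the 3 SD condition.** Assumptions: no true response; readings carry independent normal error; units are one ELISA SD. With error e₀ at baseline and eⱼ at visit j, the change is eⱼ − e₀, and with a single-reading baseline

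P(max over k visits ≥ 3) = ∫ φ(x) [1 − Φ(3 + x)^k] dx.

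For one visit this is 1 − Φ(3/√2) = 1 − Φ(2.12) = 1.7%. For a baseline that is the mean of two readings, x inside Φ is multiplied by √0.5. For a noise-free baseline the result is 1 − Φ(3)^k = 1 − 0.99865^k.

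| Assumption | One visit | Best of 11 |
|---|---|---|
| SD is that of one reading, single-reading baseline | 1.7% | 11.1% (simulation of 1,000,000 patients: 11.0%) |
| Same, baseline the mean of two readings | 0.7% | 6.3% |
| Baseline free of noise | 0.13% | 1.5% |
| SD is that of the difference, shared baseline | 0.13% | 1.2% |
| Within-patient SD 1.25 times the assay SD, single-reading baseline | 4.5% | 23.9% |

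In the first row, 9 visits instead of 11 give 9.8%. Applied to 60 placebo patients, 11.1% is 60 × 0.111 = 6.7 patients, and 1.5% is 60 × 0.015 = 0.9.

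The documents do not say which row applies. SAP section 3 takes the last non-missing value before the first dose as baseline, which points to a single reading. Protocol 7.2.2 says the V0 backup sample is used together with V1 for pre-treatment levels, which could mean two. All rows concern the 3 SD condition alone; pre-adsorption would lower them by an amount that cannot be computed here.

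**5. What exists for placebo.** The mITT set (SAP 3.1.2) requires, in both arms, a baseline and at least one post-baseline OD without pre-adsorption. The 3 SD component can therefore be computed for placebo without new data once the ELISA SD is given. Whether placebo samples were run with pre-adsorption is not stated.

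**The case against.** The strongest reply is that this output is descriptive and little depends on it. The responder rate is not a primary or secondary efficacy variable, not a success criterion and not part of the sample size. The confirmatory test compares the mean maximal increment between arms, so any gain from taking the best of several visits is in the control as well. The MMRM gives differences by visit. All of this stands. A reader might infer that the maximum inflates the type I error of the primary test, or that the responder rate is the headline immunogenicity result; the documents support neither.

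A second reply concerns the 11%. It holds for the 3 SD condition alone, for an ever-responder, with a single-reading baseline and an ELISA SD that nobody has stated. If the SAP table is truly per visit, 1.7% or less is the relevant figure under the first three assumptions in the table. This also stands. It would be wrong to quote 11% as the false-positive rate of the trial's criterion. Noise of that size also could not explain a rate near the 87.5% of Phase I.

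Third, 7.2.1.1 speaks of a specific antibody signal and may be shorthand for the full rule in 9.1.2.1, while table specifications sit in documents not available here. This is possible but does not close the gap. Protocol 7.1.1.1 attaches the same adjective to the primary variable, which protocol 9.2 and SAP 3.1.2 take without pre-adsorption. The word therefore does not imply the second condition, and someone programming from 7.2.1.1 would not apply it.

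Finally, the placebo rate is not beyond recovery: the OD listing would allow the 3 SD part to be derived later, given the ELISA SD. That is a reason to plan the table now. The both-arm table already planned uses a different threshold and does not supply it.

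**Conclusion.** The point holds as a defect in a descriptive output. Responders are reported in one arm only. The SAP leaves the term undefined, and the protocol's two definitions can classify the same patient differently. The by-visit layout does not match the maximum on which both definitions rest.

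The size of the noise floor is not known. Under independent normal assay error and the 3 SD condition alone, it runs from about 1% to about 24% for best of 11, depending on what the ELISA SD measures, how baseline is formed and whether there is within-patient variation beyond the assay. These are illustrations and not estimates for this trial. The uncertainty is itself the case for a placebo column, because the placebo arm measures the rate directly.

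The primary analysis, its error rate and the trial's success criterion are not affected.

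**What to change.** 1. Put the 9.1.2.1 definition (both conditions) in SAP 6.1.1 and align protocol 7.2.1.1 with it.
2. State the ELISA SD, what it is the SD of (one reading or a difference), and whether the pre-treatment value is one reading or a mean.
3. Report the ever-responder rate, based on the maximal increment, separately from any per-visit rate. If a per-visit rate is kept, say how the pre-adsorption condition applies at visits other than that of the maximum.
4. Tabulate both rates for ABvac40 and placebo, with the difference and its 95% CI. With 60 placebo patients, 0 responders gives an exact 95% interval of 0 to 6.0%, and 6 responders gives 3.8% to 20.5%, enough to tell a negligible noise floor from a material one.

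The cost is one definition and one extra column. If placebo samples were not run with pre-adsorption, report the 3 SD component for both arms alongside the full definition for ABvac40. That fallback leaves the full rule uncontrolled, but it gives a controlled figure for the part most exposed to noise and the one closest to the Phase I rule.
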